Computer-Assisted Surgery for Internal Fixation of Peritrochanteric Femur Fractures: A Randomized Controlled Study

NCT04528459

IRB approval: December 9, 2020

BACKGROUND

Peritrochanteric femur fractures are the most common type of fracture requiring orthopaedic surgical intervention. Successful surgery with cephalomedullary nail fixation can restore patients' baseline ambulatory function and prevent complications resulting from prolonged bedrest and immobilization. However, failure of fixation due to lag screw cut-out has an incidence rate of nearly 8% following open reduction internal fixation with an cephalomedullary nail. Given this high rate of failure, prior investigations have identified the strongest predictor of screw cut-out following cephalomedullary nail fixation, tip-apex distance (TAD) of the lag screw. TAD is defined as the sum of the distance from the tip of the lag screw to the apex of the femoral head on the anteroposterior and lateral radiographs. A TAD distance of greater than 25mm has been shown to be a strong predictor of screw cut-out and fixation failure. Although use of intraoperative two-dimensional (2D) fluoroscopy helps guide the operator on optimal lag screw placement, the femoral head is a three-dimensional (3D) spherical anatomic structure that is difficult to visualize using fluoroscopy alone. Computer navigation platforms have been developed to help reliably obtain a TAD of less than 25 mm, potentially reducing the risk of lag screw cut-out and failure. To date, however, only one clinical study has compared computer navigation to traditional fluoroscopy in achieving a TAD of less than 25 mm (Herzog et al. 2019). While this study demonstrated significantly improved accuracy of lag screw placement in the computer navigation cohort with no significant effect on average operating time, the study did not assess several other important variables nor did it report rates of lag screw cut-out. Despite the potential benefits of computer navigation, fluoroscopy remains the current standard of care for inserting cephalomedullary nails in the treatment of intertrochanteric femur fractures.

The purpose of this study is to evaluate the ADAPT (Adaptive Positioning Technology, Stryker®, USA) computer navigation platform in a controlled, randomized fashion to determine its effect on TAD, lag screw cut-out, operative time, fluoroscopy time and number of Kirschner wire (K wire) passes prior to insertion of the final implanted device. Additionally, 1 year follow-up will compare postoperative complications, mobility, range of motion, social dependency and pain level between procedures that utilized the ADAPT platform and those that did not.

Study Design: This will be a prospective, randomized, double-blind, controlled trial with two treatment cohorts. Cohort 1 will consist of 30 patients with closed peritrochanteric femur fractures who undergo open reduction internal fixation with a Stryker© Gamma intramedullary nail using traditional fluoroscopy for insertion of the lag screw (control group). Cohort 2 will consist of 30 patients with closed peritrochanteric femur fractures who undergo open reduction internal fixation with a Stryker© Gamma intramedullary nail using the Stryker© ADAPT platform to assist with insertion of the lag screw (treatment group). Patients will be blinded to treatment group allocation as will clinicians/researchers during data processing/analysis. The primary outcome will be TAD, as measured on AP and lateral hip radiographs. Secondary outcomes will be position of the lag screw as described by Cleveland et al, operative time, fluoroscopy time, and number of K wire passes prior to final placement of the lag screw. Additionally, evidence of lag screw cut-out on hip radiographs, hip range of motion relative to the contralateral hip, mobility and social dependency as defined by the Harris Hip Score, and pain level (visual analog scale) will be assessed at 3 month, 6 month, 1 year, and 2 year follow up visits.

Statistical Procedures: Descriptive statistics will be calculated to compare patient demographics between the two cohorts. The Student t-test and the Fisher's exact test will be used to compare outcomes between the two cohorts. Based on a previous study by Herzog et al (2019), we expect the ADAPT platform to lead to an average reduction in TAD of 8 mm (24.9 mm +/- 6.68 mm without ADAPT vs. 16.9 mm +/- 6.30 mm with ADAPT). Accordingly, in order to achieve a power of 0.8 with an alpha of 0.05 and a beta of 0.2, we will need to accrue 11 patients per cohort. Our plan is to enroll 30 patients per cohort.

RESEARCH AIMS & ABSTRACTS

Research Question(s)/Hypothesis(es): We hypothesize that use of the ADAPTTM platform will lead to a lower mean TAD and a greater proportion of patients with a TAD of 25 mm or less. We do not expect a difference in the proportion of patients with optimal lag-screw position within the femoral head as defined by Cleveland et al. Use of the ADAPT platform will lead to no difference in operative time or blood loss, decreased fluoroscopy use, and fewer K wire passes. In terms of radiographic evidence of screw cut-out, we expect no difference at any

of the follow up visit time points. Additionally, we expect no difference in hip range of motion, mobility and social dependency as defined by the Harris Hip Score, or pain level at any of the follow up visit time points.

Scientific Abstract: Peritrochanteric femur fractures are the most common type of fracture requiring orthopaedic surgical intervention. Successful treatment with cephalomedullary nail fixation can restore patients' baseline ambulatory function and prevent complications associated with prolonged bedrest and immobilization. However, failure of fixation due to lag screw cut-out has an incidence rate of nearly 8% following open reduction internal fixation with a cephalomedullary nail. Previous research has identified the tip-apex distance (TAD) of the lag screw as the strongest predictor of lag screw cutout. Accordingly, computer navigation platforms have been developed to reliably achieve a TAD of less than 25 mm. To date, however, only one clinical study has compared computer navigation to traditional fluoroscopy in achieving a TAD of less than 25 mm. While this study demonstrated significantly improved accuracy of lag screw placement in the computer navigation cohort with no significant effect on average operating time, the study did not assess other important intraoperative variables nor postoperative outcomes. The purpose of this study is to determine if computer navigated lag screw placement during cephalomedullary nail fixation utilizing the novel ADAPT platform will lead to a lower mean TAD and a greater proportion of patients with a TAD of 25 mm or less. This will be a prospective, randomized, single-blinded, controlled trial with two treatment cohorts. Cohort 1 will consist of patients with closed peritrochanteric femur fractures who undergo open reduction internal fixation with a Stryker[©] Gamma cephalomedullary nail using traditional fluoroscopy for insertion of the lag screw. Cohort 2 will consist of patients with closed peritrochanteric femur fractures who undergo open reduction internal fixation with a Stryker[©] Gamma cephalomedullary nail using the Stryker[©] ADAPT platform to assist with insertion of the lag screw. Patients will be blinded to treatment group allocation but clinicians/researchers will not. The primary outcome will be TAD as measured on postoperative AP and lateral hip radiographs. Secondary outcomes will be position of the lag screw as described by Cleveland et al, operative time, fluoroscopy time, and number of K wire passes prior to final placement of the lag screw. Additionally, evidence of lag screw cut-out on postoperative hip radiographs, hip range of motion relative to the contralateral hip, mobility and social dependency as defined by the Harris Hip Score, and pain level will be assessed at 3 month, 6 month, 1 year, and 2 year follow up

visits. Student t-test and Fisher's exact test will be used to compare outcomes between the two cohorts.

Hip fractures are common injuries in which the top part of the femur bone breaks. These fractures often require surgery and are frequently treated with a metal rod that goes inside the femur, known as a cephalomedullary nail. Successful treatment of hip fractures with a cephalomedullary nail can allow patients to start walking soon after surgery. However, the cephalomedullary nail must be inserted into the correct position in the femur, otherwise it may not work properly. Traditionally, surgeons use x-rays in the operating room to determine if a cephalomedullary nail is in the correct position within the femur. Recently, however, computer navigation technology has been developed to help surgeons correctly position cephalomedullary nail devices. To date, only one study has compared x-rays to computer navigation technology in the treatment of hip fractures. While this study demonstrated more accurate placement of the cephalomedullary nail with computer navigation, the study did not consider other important outcomes such as radiation exposure, hip function and pain after surgery. The purpose of this study is to further compare x-rays and computer navigation (the ADAPT platform) for the placement of a cephalomedullary nail when treating hip fractures. This study will have two groups: group 1 will consist of patients with hip fractures who undergo surgery with a cephalomedullary nail using only x-rays, and group 2 will consist of patients with hip fractures who also undergo surgery with a cephalomedullary nail but using computer navigation (the ADAPT platform) as well as x-rays. X-rays taken after surgery will be used to compare the average position of the cephalomedullary nail in the femur between the two groups. Other variables will also be compared between the two groups including the average time required to perform the surgery, the average number of x-rays taken during the surgery, the average number of attempts required to position the cephalomedullary nail, as well as the occurrence of signs on x-ray that suggest the cephalomedullary nail is not functioning properly, average hip range of motion, mobility, independence, and pain at 3 months, 6 months, 1 year and 2 years after surgery.

REFERENCES

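### Does wording the groups by technique used allow switched ADAPT cases to leave their randomised arm in the analysis?

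*Combined protocol and SAP*

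**What the plan says.** The purpose paragraph of the Background sets out two things. First, the ADAPT platform is to be evaluated "in a controlled, randomized fashion to determine its effect on TAD", together with cut-out, operative time, fluoroscopy time and K-wire passes. Second, complications, mobility, range of motion, dependency and pain at 1 year are to be compared "between procedures that utilized the ADAPT platform and those that did not".

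Study Design describes the arms by what is done to the patients. Cohort 1 has the nail inserted "using traditional fluoroscopy for insertion of the lag screw (control group", as its label reads. For the other arm, "Cohort 2 will consist of 30 patients with closed peritrochanteric femur fractures who undergo open reduction internal fixation" with ADAPT, labelled the treatment group. The Scientific Abstract repeats this form: "Cohort 2 will consist of patients with closed peritrochanteric femur fractures who undergo open reduction internal fixation". The lay summary that follows it says that "group 1 will consist of patients with hip fractures who undergo surgery with a cephalomedullary nail using only x-rays", and that "X-rays taken after surgery will be used to compare the average position of the cephalomedullary nail in the femur between the two groups".

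The only test rule is in Statistical Procedures: "The Student t-test and the Fisher's exact test will be used to compare outcomes between the two cohorts". The same paragraph plans to enrol 30 patients in each cohort. Allocation is mentioned only in the blinding statements. No section names an analysis population, and none mentions a change of technique during surgery.

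**The concern.** Assignment and use are different criteria. The follow-up sentence takes the procedure as its unit and use of ADAPT as its criterion. The cohort descriptions are also phrased by technique, and the test rule refers back to those cohorts. Read literally, a patient randomised to ADAPT whose operation was done by fluoroscopy alone would fit the description of the control group. An analyst might count that patient there or leave the patient out.

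Switching is physically possible, because the lay summary says that ADAPT cases use x-rays as well as navigation. If surgeons gave up navigation mainly in difficult cases, and those cases ended with a longer TAD, moving or removing them would make ADAPT look better than it is. Fluoroscopy time and K-wire passes could be affected in the same way. At stake would be the protection that randomisation gives to the primary comparison.

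**Working it through.** **1. What each passage governs.**

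| Place | Wording | Does it decide who is analysed where for TAD? |
|---|---|---|
| Purpose paragraph, first sentence | randomised evaluation of TAD | Points to assigned arm |
| Purpose paragraph, second sentence | by use of ADAPT | No; covers 1-year outcomes only |
| Study Design and Scientific Abstract | cohorts described by technique; Study Design labels them control and treatment | Ordinary description of arms |
| Statistical Procedures | test between the two cohorts, 30 enrolled in each | Yes; cohort size is set at enrolment |
| Lay summary | x-rays alone against navigation plus x-rays | No; explains the two techniques |

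Patients are normally enrolled before surgery. A cohort of 30 fixed by enrolment is an assigned arm, and reclassifying by technique would break the planned 30 and 30.

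**2. The plan's own figure.** Inputs from Statistical Procedures: difference 8 mm (24.9 − 16.9), SDs 6.68 and 6.30, power 0.80, alpha 0.05 (two-sided assumed).
- Pooled SD = √((6.68² + 6.30²)/2) = 6.49.
- n = 2 × (1.96 + 0.84)² × 6.49² / 8² ≈ 10.3, so 11 per cohort, as stated.
- Under the noncentral t distribution, 11 per cohort gives power 0.785 and 12 gives 0.822. At the planned 30, power is 0.997.

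The analysis-population question does not affect the required n.

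**3. Possible bias with no true effect.** The document gives no switch rate and no TAD shift, so both are assumed. Let a share p of cases in each arm be difficult, with TAD longer by h, and let every difficult ADAPT case switch.
- Switched cases dropped: bias = h × p.
- Switched cases counted as control: bias = h × 2p/(1 + p).
- Analysed as randomised: bias = 0.

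Rejection rates are from 40,000 simulated trials per scenario (30 per arm, SD 6.5, two-sided Student t-test at 0.05).

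| p, h | Counted as control | Rejects | Dropped | Rejects |
|---|---|---|---|---|
| 10%, 5 mm | 5 × 0.2/1.1 = 0.91 mm | 7.9% | 0.5 mm | 5.9% |
| 10%, 8 mm | 8 × 0.2/1.1 = 1.45 mm | 11.9% | 0.8 mm | 7.2% |
| 20%, 5 mm | 5 × 0.4/1.2 = 1.67 mm | 14.5% | 1.0 mm | 8.2% |
| 20%, 8 mm | 8 × 0.4/1.2 = 2.67 mm | 27.3% | 1.6 mm | 12.7% |

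If only half of the difficult ADAPT cases switch, the range runs from (10%, 5 mm) to (20%, 8 mm):
- Counted as control: 5 × (0.15/1.05 − 0.05/0.95) = 0.45 mm to 8 × (0.3/1.1 − 0.1/0.9) = 1.29 mm. Simulated rejection is 5.8–9.9%.
- Dropped: 5 × (0.1 − 0.05/0.95) = 0.24 mm to 8 × (0.2 − 0.1/0.9) = 0.71 mm. Simulated rejection is 5.2–6.4%.

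If switching is unrelated to TAD, the bias is 0 mm and rejection is 4.8–5.1%.

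**4. With the planned 8 mm benefit,** and none in switched cases (all difficult cases switching):
- As randomised: 8 × (1 − p) = 7.2 mm at 10% and 6.4 mm at 20%.
- Dropped: 8 + h × p = 8.5 to 9.6 mm.
- Counted as control: 8 + h × 2p/(1 + p) = 8.9 to 10.7 mm (simulated 8.9 to 10.6).
- Simulated power as randomised, in the order of the table: 96.4%, 94.7%, 88.7% and 83.3%. All exceed the planned 80%.

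**5. Does the literal wording produce this bias?** The bias needs switching driven by difficulty. Difficulty met while placing the screw usually appears after ADAPT has been started. Such a procedure has still used the platform, so under the follow-up sentence it stays in the ADAPT group. It was not done with x-rays alone either, so it does not fit the lay description of group 1. A case in which ADAPT was never started, for instance because equipment was unavailable, fits the non-ADAPT wording cleanly. It has no evident link to TAD, and the bias is then 0 mm.

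**The case for a change.** The strongest reply is that randomisation describes how patients are assigned, not how they are analysed. The one sentence that spells out a comparison does so by use. The Scientific Abstract leaves clinicians unblinded, so a later decision about a switched case could be made with the arm known. One written sentence would remove the doubt at almost no cost. A surgeon might also forgo navigation from the outset in a fracture that looks difficult. That case would fit the non-ADAPT wording and would be related to outcome.

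Part of this stands. The analysis population is unstated, and the follow-up sentence is loosely worded. The route through a choice made before surgery is possible in principle, although the document provides for no such choice.

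It does not follow that the plan prescribes, or leans towards, as-treated analysis of TAD. The loose sentence leaves TAD out, and the sentence before it puts TAD under randomised evaluation. No wording excludes an enrolled patient, so the idea that cases might be dropped rests on silence alone. Study Design also says that researchers are blinded during data processing and analysis. That differs from the abstract, but the difference is a separate matter.

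**Conclusion.** The concern does not call for a change. In a randomised trial with cohorts fixed at enrolment, labelled control and treatment, and compared as cohorts, an analyst would keep patients in their assigned arms. The missing statement is detail that analysts fill sensibly. The follow-up sentence is loose phrasing in a purpose paragraph.

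The largest figure, a 27% false-positive rate, needs five things together: 20% difficult cases, an 8 mm longer TAD in them, every difficult ADAPT case switching, all of them counted as control, and no true effect. Half the switching with cases dropped gives 5–6%. Switching that is absent or unrelated to TAD gives the nominal 5%. With the planned 8 mm effect, the choice of analysis population alters the estimate (6.4–7.2 mm as randomised, against 8.5–10.7 mm otherwise) but probably not the conclusion.

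This rests on reading cohort as assigned arm and on the document's silence about any switching. Evidence that outcome-related switching was expected would make the point worth reopening.

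### Hip motion is scored against the other hip and compared by an unadjusted t-test; using the contralateral reading as a covariate would be at least about as precise, and possibly clearly more so

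*Combined protocol and SAP*

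**What the plan says.** The Study Design paragraph (under Background) and the Scientific Abstract both list "hip range of motion relative to the contralateral hip" among the outcomes assessed at four follow-up visits from 3 months to 2 years. It comes after the named primary outcome (TAD) and the named secondary outcomes. Neither place says whether the score is a difference or a ratio, or states outright when the contralateral hip is measured.

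The Statistical Procedures paragraph gives one general sentence on analysis: "The Student t-test and the Fisher's exact test will be used to compare outcomes between the two cohorts". The Scientific Abstract ends by naming the same two tests. No covariate or regression model appears anywhere. The hypothesis section says "we expect no difference in hip range of motion", without a margin. The lay abstract refers to "average hip range of motion, mobility, independence, and pain at 3 months". The sample size is justified for TAD only, and no SD, correlation or target difference is given for hip motion.

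**The concern.** A side-to-side score fixes in advance how the contralateral reading enters the comparison: it is subtracted in full or used as a divisor. That is efficient only when the two hips track each other closely enough. If they correlate weakly, subtraction brings in the other hip's variation without removing much of the operated hip's own, and the score can be noisier than the operated hip alone. A linear model lets the data set the weight.

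At stake is the width of the interval for the between-arm difference in hip motion. The plan expects no difference here, and its cohort size was not chosen for this outcome, so precision is worth having if it costs little. Leaving the score as either a difference or a ratio also leaves open which variable will be analysed.

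**Working it through.** **The plan's own figure.** The only sample size calculation is for TAD: "average reduction in TAD of 8 mm", with "24.9 mm +/- 6.68 mm without ADAPT vs. 16.9 mm +/- 6.30 mm with ADAPT", at "a power of 0.8 with an alpha of 0.05". Pooled SD = √((6.68² + 6.30²)/2) = 6.49 mm. The two-sided normal formula gives n = 2 × (1.960 + 0.842)² × 6.49²/8² ≈ 10.3, so 11 per cohort as stated. (The t-based answer is 11.4, so 12.) The figure reproduces but says nothing about hip motion.

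**Inputs for hip motion.**
- From the plan: 30 per cohort.
- Assumed, because the documents give no values: complete data; between-hip correlation r; k = contralateral SD / operated SD.

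**Formulas**, with the operated-hip variance set to 1:
- Operated hip alone: 1
- Side-to-side difference: 1 + k² − 2rk, which is 2(1 − r) at k = 1
- Linear model with contralateral motion as covariate, large sample: 1 − r²

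The difference exceeds the model by (1 + k² − 2rk) − (1 − r²) = (k − r)², and the operated hip alone exceeds it by r². Neither can be negative, so in large samples the model is never less precise than either. The difference is noisier than the operated hip alone when r < k/2, that is below 0.5, 0.4 and 0.3 at k = 1, 0.8 and 0.6.

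**Cost at this size.** Estimating the slope multiplies the model's variance by 1 + 1/(60 − 4) = 1 + 1/56, or 1.8%. The last column includes this.

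| k | r | Difference | Model (large sample) | Saving (large sample) | Difference/model variance, 30 per cohort |
|---|---|---|---|---|---|
| 1 | 0.3 | 1.40 | 0.91 | 35% | 1.51 |
| 1 | 0.5 | 1.00 | 0.75 | 25% | 1.31 |
| 1 | 0.7 | 0.60 | 0.51 | 15% | 1.16 |
| 1 | 0.8 | 0.40 | 0.36 | 10% | 1.09 |
| 1 | 0.9 | 0.20 | 0.19 | 5% | 1.03 |
| 0.8 | 0.3 | 1.16 | 0.91 | 22% | 1.25 |
| 0.8 | 0.5 | 0.84 | 0.75 | 11% | 1.10 |
| 0.8 | 0.7 | 0.52 | 0.51 | 2% | 1.00 |
| 0.6 | 0.3 | 1.00 | 0.91 | 9% | 1.08 |
| 0.6 | 0.5 | 0.76 | 0.75 | 1% | 1.00 |
| 0.6 | 0.7 | 0.52 | 0.51 | 2% | 1.00 |

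Once the slope is paid for, the 1–2% savings vanish. Where the true slope r/k equals 1 (for example k = r = 0.8), the ratio is 0.98: the model is about 2% worse in variance. Against the operated hip alone, the model gains once r exceeds about 0.14. At r = 0 its interval is about 1% wider (half-width 0.522 against 0.517 SD).

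**In terms of intervals and power** (k = 1, 30 per cohort, operated hip alone / difference / model):
- 95% CI half-width in SD units: 0.517 / 0.612 / 0.498 at r = 0.3; 0.517 / 0.517 / 0.452 at r = 0.5; 0.517 / 0.400 / 0.373 at r = 0.7. The model's interval is therefore about 19, 13 and 7% narrower than the difference's.
- Power for an assumed 0.5 SD arm difference: 48 / 36 / 51% at r = 0.3; 48 / 48 / 59% at r = 0.5; 48 / 69 / 75% at r = 0.7.

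A simulation of 20,000 trials agrees. The standard errors were 0.258 / 0.304 / 0.248 at r = 0.3 and 0.256 / 0.199 / 0.185 at r = 0.7.

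**If the score is a ratio.** With an assumed 15% coefficient of variation in each hip, the ratio's is 18.6% at r = 0.3 and 12.1% at r = 0.7. The pattern is the same: noisier than the operated hip alone at low correlation, better at high.

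**The case against.** The strongest reply is that nothing here is an error. Under randomisation an unadjusted t-test on a side-to-side score is valid, the outcome is neither primary nor among the named secondaries, and neither the sample size nor the main conclusion depends on it. All of that stands, and it limits the point to an inexpensive improvement.

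The size of the gain is also uncertain. A reader might take 35, 25 and 15% as the saving to expect, but those figures need equal SDs in both hips, which the documents do not give. At k = 0.8 or 0.6 much or all of the gain disappears. At k = 1 with r of 0.8 to 0.9, the difference score's excess variance is only about 3 to 9%. If k exceeded 1 the gain would be larger.

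A reader might also call the covariate free and never worse. That is exact only in large samples; here it can cost about 2% in variance.

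The model uses a contralateral reading that, on the natural reading of the plan, is taken at the follow-up visit and so after randomisation. That needs stating, but the planned score relies on the same assumption.

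Finally, a reader might infer that the documents define the outcome in two conflicting ways, because the hypothesis and lay abstract mention plain hip motion. This is better read as shorthand: the hypothesis section also shortens the pain measure, which Study Design specifies as a visual analog scale. The genuine gap is difference versus ratio.

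**Conclusion.** The point holds as a matter of precision and of completing a definition. The planned comparison is valid, but a covariate model uses the same readings at least as well in large samples and costs at most about 2% in variance at 30 per cohort with complete data. Over the assumed grid, the large-sample variance reduction against the difference score runs from about 1% to 35%. At the lower end the slope's cost cancels it. The documents give neither r nor k, so no single figure can be claimed.

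Two stronger readings are not supported. The planned t-test is not biased, and a stiff or replaced contralateral hip would add noise to the score without favouring an arm under randomisation. Nor does the model make the expected absence of a difference demonstrable: that would need a margin, which is a separate matter. The TAD analysis and its sample size are unaffected.

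**What to change.** In Statistical Procedures:
- Define the outcome once, as range of motion of the operated hip in degrees.
- At each visit, compare arms with a linear model containing arm and contralateral hip motion, and report the adjusted difference with its 95% CI.
- Show the side-to-side value descriptively, and say whether it is a difference or a ratio.
- State when the contralateral hip is measured and, if at follow-up, the assumption that treatment does not affect that hip.

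The score as described implies that both hips are already measured, so this needs a change of wording and no new measurement. The price is one degree of freedom and a modelling assumption (a linear relation with a common slope). A sensitivity analysis leaving out patients with a diseased or replaced contralateral hip would be reasonable, but it needs a data item that the documents do not list. It is therefore an optional addition with its own cost.

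### Does naming two TAD results in the hypothesis, with no rule for a disagreement, leave the trial's main conclusion open?

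*Combined protocol and SAP*

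**What the plan says.** Two places name two TAD results. Under Research Question(s)/Hypothesis(es), ADAPT "will lead to a lower mean TAD and a greater proportion of patients with a TAD of 25 mm or less". The purpose sentence in the Scientific Abstract repeats this: the "novel ADAPT platform will lead to a lower mean TAD and a greater proportion of patients with a TAD of 25 mm or less".

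Elsewhere there is one result or an unspecified one:

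- The Scientific Abstract states: "The primary outcome will be TAD as measured on postoperative AP and lateral hip radiographs". Study Design in the Background also gives TAD as the primary outcome. Neither names a mean or a proportion, and neither list of secondary outcomes includes the 25 mm proportion.
- Statistical Procedures sizes the trial on the mean: "we expect the ADAPT platform to lead to an average reduction in TAD of 8 mm", with SDs of 6.68 mm without ADAPT and 6.30 mm with it. The conclusion is that "we will need to accrue 11 patients per cohort. Our plan is to enroll 30 patients per cohort".
- The tests are named together, without assignment: "The Student t-test and the Fisher's exact test will be used to compare outcomes between the two cohorts".
- The lay abstract mentions only an average: "X-rays taken after surgery will be used to compare the average position of the cephalomedullary nail in the femur between the two groups".

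The purpose paragraph in the Background is broader than the one in the Scientific Abstract. It lists the effect on TAD among several outcomes and mentions neither the mean nor the 25 mm threshold.

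**The concern.** Read strictly, the word *and* in the hypothesis requires both results. The sample size and the lay abstract point to the mean alone. If the mean differs significantly and the 25 mm proportion does not, the first reading says the hypothesis was not confirmed and the second says it was. The reading could then be chosen after the data are seen.

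The choice would not be trivial. The Background ties the risk of cut-out to a TAD above 25 mm, so the proportion carries the clinical argument while the mean carries the sample size. A dichotomised measure also has less power than the mean it is cut from, so disagreement in that direction can be expected in some trials.

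**Working it through.** **Inputs from Statistical Procedures.** Means are 24.9 mm (control) and 16.9 mm (ADAPT), SDs 6.68 and 6.30 mm, alpha 0.05, power 0.8, and 30 per cohort planned. Assumed because not stated: two-sided tests, normal TAD, no dropout.

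**1. The plan's own figure.** Pooled SD = √[(6.68² + 6.30²)/2] = √42.156 = 6.49 mm. Then

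n = 2 × (1.960 + 0.842)² × 42.156 / 8² = 10.3, rounded up to 11 per cohort.

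This matches the stated 11. The noncentral-t version gives 11.39, hence 12. At 30 per cohort the t-test has 99.7% power for 8 mm.

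**2. The proportion implied by the same figures.**

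- Control: Φ[(25 − 24.9)/6.68] = Φ(0.015) = 50.6%.
- ADAPT: Φ[(25 − 16.9)/6.30] = Φ(1.286) = 90.1%.

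The exact power of Fisher's test at 30 per cohort is 90.7%.

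**3. How often the tests disagree.** For each row, 200,000 trials were simulated with 30 per cohort and the control mean held at 24.9 mm. The pooled t-test was applied to TAD and Fisher's exact test to TAD ≤ 25 mm, each counted only when significant in favour of ADAPT.

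| True reduction | Mean | Proportion | Both | Mean only | Proportion only | Disagree |
|---|---|---|---|---|---|---|
| 8 mm (plan) | 99.7% | 90.7% | 90.7% | 9.0% | 0.03% | 9.1% |
| 6 mm (assumed) | 94.0% | 70.4% | 69.9% | 24.1% | 0.5% | 24.6% |
| 5 mm (assumed) | 83.5% | 54.3% | 53.1% | 30.4% | 1.2% | 31.5% |
| 4.5 mm (assumed) | 75.1% | 45.6% | 44.0% | 31.1% | 1.6% | 32.6% |
| 4 mm (assumed) | 65.1% | 36.8% | 34.9% | 30.2% | 1.9% | 32.1% |

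With lognormal TAD of the same means and SDs, disagreement is 19% at 8 mm, 37% at 5 mm and 35% at 4 mm.

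**4. What a free choice of reading could cost in error rate.** With equal means (reduction 0), the t-test favours ADAPT in 2.445% of trials, Fisher's test in 1.371%, and both in 0.761%. Either one does so in 2.445 + 1.371 − 0.761 = 3.055%. Accepting either result therefore raises false success from about 2.4% to about 3.1%. Requiring both lowers it to about 0.8%.

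**5. What the text supports.** The Background defines TAD as a sum of two distances, a continuous measure. Study Design makes TAD the only primary outcome. Statistical Procedures sizes the trial on its mean difference and names a Student t-test. Together these identify the primary comparison as the t-test on mean TAD. Fisher's exact test fits the yes/no outcomes, of which the 25 mm threshold is one.

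The hypothesis paragraph continues with expectations on screw position, operative time, blood loss, fluoroscopy use, K wire passes, cut-out, range of motion, Harris Hip Score and pain. That is a list of expectations, and nobody would read it as one joint test. Within such a list, *and* between two TAD results is ordinary prose and not a decision rule.

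**The case for a change.** The strongest case for a change is that the mean's rank has to be inferred, and that the purpose sentence in the Scientific Abstract gives the threshold equal standing with it. Reporting both results does not by itself say whether the stated hypothesis was confirmed. Disagreement also does not depend only on a smaller effect. If the reduction is the full 8 mm but the control mean is 20.9 mm (assumed), the tests disagree in about 34% of trials, and with a control mean of 22.9 mm (also assumed) in 16.6%. A clarification would cost one sentence and no patients.

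Much of this stands as description. The documents do not rank the 25 mm proportion, do not assign the tests, and do not say how a disagreement is read. The 9% figure is not an upper bound, since the lognormal version doubles it.

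What does not stand is the step from there to opposite answers from the same data. That needs *and* to be a decision rule, which no section states. Read as two expectations, a disagreement has one plain report: lower mean TAD shown, greater proportion at 25 mm or less not shown. Both estimates would be in front of the reader. The lay abstract adds little, since it is a plain-language summary that neither names TAD nor states a hypothesis.

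Nor do the documents dictate one rule for the two-part claim. Testing the mean first and then the proportion, or requiring both as co-primary, sets the same bar for that claim. Yet when only the mean is significant, the first calls the primary result positive and the second calls it negative. Adding either would be a choice of convention and would not correct an error.

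**Conclusion.** The concern does not call for a change. The gap is one of detail, and analysts would fill it sensibly: mean TAD by t-test as the primary comparison, the 25 mm proportion by Fisher's exact test beside it, each reported on its own terms. A sentence saying so would be tidy, but it would alter no test, estimate or sample size.

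On the plan's figures at 30 per cohort, power is 99.7% for the mean and about 91% for both results together. The tests disagree in about 9% of trials under normality and about 19% under a lognormal shape, almost always with only the mean significant. Higher rates rest on assumed values outside the plan: 31% to 33% under normality for a true reduction of 4 to 5 mm, or about 34% for a control mean of 20.9 mm. The error-rate cost of the looseness is small, about 3.1% against 2.4%. These figures assume two-sided tests at 0.05, no dropout and the plan's SDs.
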